Pneumo-CLL study: Immunogenicity of the Currently Recommended Pneumococcal Vaccination Schedule in Patients with Chronic Lymphocytic Leukaemia.

PROTOCOL

Principal Investigator:	[name]
Co-investigator:	[name]
Writing committee:	[name]
	[name]
	[name]
	[name]
	[name]
	[name]
	[name]
	[name]
	[name]
	[name]
	[name]
	[name]
	[name]

1. Introduction

Patients with chronic lymphocytic leukaemia (CLL) are at increased risk of both invasive pneumococcal disease (IPD) and community acquired pneumonia (CAP) caused by Streptococcus pneumoniae [1-3]. Therefore, international guidelines recommend pneumococcal vaccination for all CLL patients, preferably before initiation of treatment. The recommended vaccination schedule consists of Prevenar13®, a 13-valent pneumococcal conjugated vaccine (PCV13) followed 2 months later by Pneumovax23, a 23-valent polysaccharide vaccine (PPSV23) [4, 5].

The immunological efficacy of this sequential vaccination schedule in CLL patients is unknown. Previous studies have only investigated responses to either PCV13 or PPSV23 alone (Table 1) [6-15]. Responses to PPSV23 alone are poor in CLL patients [7, 9, 10, 14, 15]. Responses to the 7valent pneumococcal conjugated vaccine (PCV7) or PCV13 are higher compared to responses to PPSV23, but lower compared to responses in healthy individuals [6, 8, 15]. More advanced disease stage and lower baseline IgG negatively influence responses to vaccination (Table 1) [6, 14, 15].

Study	Year	N (final	Population	Vaccination schedule	Serologic respone definition	Response rate	Factors associated with response	
analysis) A) Studies investigating schedules containing conjugated vaccines (PCV7/PCV13)								
Sinisalo et al (8)	2007	73	n=49 CLL (15% steroids, 22% chemo, 80% Binet A, median disease duration 2 years); n=24 healthy	PCV7 only	≥ 2 fold IgG rise AND serotype specific IgG ≥ 0.35 mcg/I for at least 6/7 PCV7 serotypes	24% CLL; 71% controls	Less advanced disease; no past or ongoing chemotherapy; normal IgG.	
Paiarski et al (6)	2014	39	Treatment naive CLL (n=24); Healthy (n=15)	PCV13 only	≥2 fold Total anti-pneumococcal IgG	58.3% CLL; 100% controls	Lower stage of CLL, higher total IgG	
Andrick et al (11)	2017	8	n=4 CLL + ibrutinib; n= 4 CLL - ibrutinib	PCV13 only	≥2-fold increase in 3 or more out of 13 serotypes	Ibrutinib 0%; No Ibrutinib 100%	Х	
Svensson et al (15)	2018	128	Treatment naive CLL patients	PCV7 versus PPSV23 (RCT)	Serotype specific OPA titers to PCV13 serotypes > Lowel Limit of Quantification (OPA titers = interpolated reciprocal serum dilution resulting in complement- mediated killing of 50% of the assay bacteria)	PCV13: 32% ; PPSV23 21%	Less advanced disease; higher total I IgG	
Lindström et al (13)	2018	24	CLL, follow-up study of Sinisalo 2007	PCV75 years before	Serotype specific IgG≥0.35 mcg/I (per serotype)	For individual serotypes 29-71% of the patients were still protected	x	
Lindström et al (12)	2019	28	CLL (n=20); healthy controls (n=8), follow- up study of Sinisalo 2007		Serotype specific IgG for all PCV7 serotypes AND PPSV23 serotype 5 and 7	10-15%	Healthy controls had higher responses to all serotypes	
B) Studies	invest	igating PPS	SV23 only					
Hartkamp et al (14)	2001	24	57% Rai O-1; 28% prior chemothrapy; median disease duration >36 months	PPSV23	Protection: 2/3 serotypes 20% above cut-off based on reference adult hyperimmune plasma pool; Response: >2 fold increase + protection (definition above)	Response: 22% Protection: improved from 38% to 50% after vaccine;	Higher disease stage + lower baseline IgG; prior chemotherapy negatively impacted responses	
Sinisalo et al (7)	2001	27	n=14 Binet A, n=8 Binet B n=9 Binet C), median disease duration 3 years.	PPSV23	A significant proportionate change in total anti-pneumcoccal IgG (no cut off value given)	0% :-	x	
van der Velden et al (9)	2007	49	CLL >50% RAI 0; 20% previous chemotherapy	PPSV23 (with or without ranitidine)	Response =>4 fold increase in IgG to 3 serotypes; Protection: ≥0,35 mcg/ml	response; 'Protection' increased from 45%-59%	Ranitidine did not generate better responses	
Safdar et al (10)	2008	32	87% had previous chemotehrapy and 73% anti-CD20	PPSV23 (n=7); PPSV23 + G-CSF injections (n=25)	≥2-fold IgG rise and level >0.5mcg/ml for all 6 measured seorypes	0% (0-17% per individual serotype)	G-CSF did not generate better responses	

2. Objective

The aim of this observational cohort study is to assess the immunogenicity of the currently recommended vaccination schedule of PCV13 followed by PPSV23 in CLL patients.

3. Study design

As part of routine care, all adult CLL patients naïve to pneumococcal vaccination and cared for in the participating centers receive one dose of Prevenar13® followed by one dose of Pneumovax23® 2 months later. According to the current local standard of care for immunosuppressed individuals, the response to vaccination is assessed by measuring pneumococcal antibody levels before and 4-8 weeks after vaccination [16, 17]. In this non-interventional cohort study we will ask informed consent to all vaccinated CLL patients to collect their clinical data and laboratory results for study purposes.

4. Inclusion criteria

All adult CLL patients

- naïve to pneumococcal vaccination,
- having received one dose of Prevenar13®,
- followed by one dose of Pneumovax23® 2 months later,
- in whom pneumococcal antibody levels before and 4-8 weeks after vaccination are measured, and
- in whom a complete data collection is possible.

5. Data collection

After we obtain informed consent clinical data will be collected according to a standardized electronic case report form (Castor EDC). Variables included in the case report form are:

- sex
- smoking behaviour
- age at the moment of the PCV vaccine administration
- comorbidities (charlson comorbitiy index)
- before vaccination (as determined in the 6 weeks prior to vaccination)
 - Rai stage (I/II/III)
 - past or ongoing chemotherapy
 - ongoing steroid treatment
 - past or ongoing therapy with a monoclonal anti-CD20 antibody (and date of last infusion)
 - total IgG level
 - lymphocyte count, haemoglobin and platelet level
- pre-vaccination pneumococcal IgG levels
- post-vaccination pneumococcal IgG levels
- date of PCV and PPSV23 vaccine administration
- date of antibody measurements

Laboratory methods and definitions

Serotype-specific pneumococcal immunoglobulin G (IgG) concentrations to 5 pneumococcal serotypes shared across both vaccines (6B, 9V, 14, 19F, 23F) and 4 serotypes unique to PPSV23 (8, 15B, 20, 33F) will be determined in the immunology laboratory of the UMC Utrecht. A validated multiplex immunoassay will be used (Luminex® technology). Serologic response will be defined as a \geq 4-fold increase in serotype specific anti-pneumococcal IgG for \geq 70% of measured. Serologic protection will be defined as an antibody concentration \geq 1.3 mcg/ml for \geq 70% of all measured serotypes, according to the definition of the *American Academy of Allergy, Asthma & Immunology* [18]. In addition, because most previous studies (Table 1) used the WHO cut-off for protection in infants (\geq 0.35 mcg/ml) we will also analyse our data by the infant correlate of protection to be able to compare our results with previous studies [19].

6. Data Analysis

The primary outcome of the study is serologic response rate (SRR) after vaccination. Secondary outcomes of interest are serologic protection rates (SPR) after vaccination analysed by the 2 most widely accepted serologic cut-offs described above, geometric mean antibody concentrations before and after vaccination, and factors associated with response to vaccination, such as age, treatment status and disease stage. To this end, we will perform a multivariable logistic regression analysis, starting with all previously mentioned clinical variables of interest and using a stepwise backward selection method based on p-value <0.1. For data analysis, we will use IBM SPSS version 24.0 (Chicago, Illinois) software. We will apply an α significance level of 0.05. Means and standard deviations will be presented for normally distributed data, and medians and interquartile ranges for non-normally distributed data. The χ 2 test will be used for dichotomous variables and the Student t test or Mann-Whitney U test for normally or non-normally distributed continuous variables, respectively. The Wilcoxon signed-rank test will be used to compare median pre- and post-vaccination antibody concentrations.

7. Ethical considerations and privacy

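### Treatment is recorded only as it stood before vaccination, so patients who start therapy before the post-vaccination sample cannot be identified in the factor analysis

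*Combined protocol and SAP*

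**What the plan says.** Section 5 (Data collection) groups the treatment items with Rai stage, total IgG and blood counts under one heading, "before vaccination (as determined in the 6 weeks prior to vaccination"). The three treatment items are "past or ongoing chemotherapy", "ongoing steroid treatment" and "past or ongoing therapy with a monoclonal anti-CD20 antibody (and date of last infusion"). Outside that heading, the dated items are the two vaccine administrations and the antibody measurements.

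Under section 3 (Study design), patients "receive one dose of Prevenar13® followed by one dose of Pneumovax23® 2 months later", with antibody levels measured before and 4-8 weeks after vaccination. Section 4 (Inclusion criteria) repeats the schedule and does not exclude patients who start therapy during it.

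Section 6 (Data Analysis) includes among the secondary outcomes "factors associated with response to vaccination, such as age, treatment status and disease stage". It enters the clinical variables listed earlier into a backward-selected logistic regression. It has no rule or sensitivity analysis for therapy started during the schedule.

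**The concern.** The response is read well after treatment status is fixed, and nothing on the form shows what happened in between. A patient with no earlier therapy who receives PCV13 and then starts chemotherapy or anti-CD20 before PPSV23, or before the sample, is analysed alongside patients who stayed untreated throughout.

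This is foreseeable. The Introduction notes that "international guidelines recommend pneumococcal vaccination for all CLL patients, preferably before initiation of treatment", so some patients may be vaccinated with therapy in prospect, although the documents do not say how many. Table 1 gives reason to think exposure matters: a PCV7 study linked response to the absence of past or ongoing chemotherapy, a PPSV23 study found that prior chemotherapy impaired response, and a small PCV13 study reported 0% response with ibrutinib and 100% without, in four patients each.

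At stake is the treatment-status result, one of three factors that section 6 names. If therapy started mid-schedule lowers response, the untreated group looks worse than patients who remained untreated, and the association moves towards no effect.

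**Working it through.** The plan states no figure on this point and gives no sample size, so there is nothing to reproduce. There are three checks.

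**1. Length of the unrecorded interval.** Inputs from sections 3 and 4: 2 months from PCV13 to PPSV23, and 4-8 weeks from vaccination to sample. Neither the 6-week window nor the 4-8 weeks is tied to a named dose. Section 5 takes age at PCV administration, which favours PCV13 for the window. Four of the nine measured serotypes are only in PPSV23, which favours a sample after PPSV23.

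- Two months = 2 × 30.44 / 7 = 8.7 weeks.
- Window on PCV13, sample on PPSV23: 8.7 + 4 = 12.7 to 8.7 + 8 = 16.7 weeks, about 13 to 17. With two months taken as 8 weeks, 12 to 16.
- Window on PPSV23: 4 to 8 weeks.
- Status may itself be up to 6 weeks old, so the longest gap from assessment to response is 16.7 + 6 = 22.7 weeks in the first case and 8 + 6 = 14 in the second.

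The interval differs, but some of it is unrecorded under either reading.

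**2. Can therapy started between doses change the outcome?** Response (section 5, laboratory definitions) needs a 4-fold rise for at least 70% of the serotypes measured. Taking that as all nine: 0.70 × 9 = 6.3, so 7 are needed (6/9 = 66.7% falls short). Five are shared with PCV13. A patient who responds to all five still needs 7 − 5 = 2 of the four PPSV23-only serotypes, whose antigens are first given two months after PCV13. Therapy started between the doses can therefore decide responder status whatever the PCV13 response was.

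**3. Illustrative dilution.** All inputs here are assumed. Let p_u be the response rate in patients who stay untreated, p_t the rate in treated patients, p_s the rate in starters, and f the share of the untreated group who start therapy in the interval.

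- Observed untreated rate: p_o = (1 − f) p_u + f p_s.
- Odds ratio: [p_o / (1 − p_o)] / [p_t / (1 − p_t)].

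With p_u = 0.40 and p_s = p_t = 0.10:

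| f | p_o | Difference from treated (points) | Odds ratio |
|---|---|---|---|
| 0 | 40.0% | 30.0 | 6.00 |
| 2% | 39.4% | 29.4 | 5.85 |
| 5% | 38.5% | 28.5 | 5.63 |
| 10% | 37.0% | 27.0 | 5.29 |
| 20% | 34.0% | 24.0 | 4.64 |
| 30% | 31.0% | 21.0 | 4.04 |

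With 30% against 10%, the odds ratio falls from 3.86 to 3.78, 3.68, 3.50 and 3.16 at f = 2%, 5%, 10% and 20%. With 50% against 20%, it falls from 4.00 to 3.91, 3.77, 3.55 and 3.14.

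Setting p_s = p_t is the unfavourable case. If starters respond halfway between (p_s = 0.25), then at f = 10% p_o = 0.9 × 0.40 + 0.1 × 0.25 = 0.385 and the odds ratio is 5.63, the same as 5% starters with full loss.

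**The case against.** The strongest reply is that nothing is miscoded. Section 5 labels these items as pre-vaccination, and a patient untreated before PCV13 is correctly recorded as such. Factors known at the time of vaccination are a coherent set of predictors, whereas no clinician knows then who will start therapy later. This stands. A reader might infer that the treatment variable is wrong and should be replaced by status throughout the schedule. The documents do not support that: they never define treatment status that way, and classifying patients by what happens after baseline answers a different question.

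The size is also open to challenge. The response rates and start rates are assumed, and a patient who starts shortly before the sample may already have responded. At 5-10% starters the untreated rate moves by 1.5 to 3 points. With an assumed 50 untreated patients, the standard error of a 37% rate is √(0.37 × 0.63 / 50) = 6.8 points; with 100 it is 4.8. Shifts of that size would be hard to see. This stands too, and rules out calling the bias large.

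Finally, start dates might be retrieved later from the medical records, so the loss need not be permanent. That is fair, but the protocol does not plan it.

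What the objections leave untouched is the missing information. Without the item, the investigators can neither count the starters nor show that their effect is negligible.

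**Conclusion.** The point holds as a gap in data collection that affects a secondary analysis. Therapy started after the pre-vaccination window is neither recorded, excluded nor examined, for about 13-17 weeks on the likelier reading of the anchors and 4-8 weeks if the window refers to PPSV23.

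It concerns patients without earlier therapy; those with past chemotherapy or anti-CD20 already count as exposed to that therapy. The recorded date of last anti-CD20 infusion does not close the gap, because it covers one drug class and sits under the pre-vaccination heading.

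The direction, dilution of the treatment-status association, depends on therapy lowering response. The amount cannot be derived from the documents. The illustration runs from slight (6.0 to 5.85 at 2% starters) to noticeable (6.0 to 4.0 at 30%), with no basis for choosing between them.

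A reader might also infer that the primary response rate is compromised, or that the study fails to answer a question about vaccination before treatment. Neither follows. The primary rate describes everyone vaccinated and is not misclassified, although it includes starters unidentified. The objective in section 2 is the immunogenicity of the schedule in CLL patients; the preference for vaccinating before treatment is reported only as background.

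**What to change.** Add one item to the section 5 case report form: *CLL-directed therapy or steroids started between PCV13 and the post-vaccination sample (yes/no, type, start date)*. Naming PCV13 also removes the dependence on which dose the word vaccination refers to.

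Keep pre-vaccination treatment status as the main predictor, and keep all patients in the primary response rate. Add to section 6:

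- the number of patients who started therapy in the interval; and
- a sensitivity analysis that repeats the treatment-status comparison and the response rate with these patients separated out, labelled as conditioning on a post-baseline event.

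The cost is one or two fields from clinical data already being collected, and a sentence or two in section 6. No visit, procedure or treatment changes. The drawbacks are slightly more record abstraction and a subgroup that may be too small for more than description.

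### The case report form list has no item for ibrutinib or other CLL therapy beyond chemotherapy, steroids and anti-CD20, so the secondary factor analysis cannot report or adjust for it

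*Combined protocol and SAP*

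**What the plan says.** Section 5 of the combined protocol and SAP introduces its list with "Variables included in the case report form are", followed by named items and no open-ended entry. Three of them concern treatment: chemotherapy (past or current), steroids (current only), and "past or ongoing therapy with a monoclonal anti-CD20 antibody (and date of last infusion"). The treatment items are recorded as they stood before vaccination.

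Section 3 describes the population as "all adult CLL patients" not previously vaccinated against pneumococcus, and section 4 sets no restriction on treatment.

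Section 6 names as a secondary outcome "factors associated with response to vaccination, such as age, treatment status and disease stage". The logistic regression is built by "starting with all previously mentioned clinical variables of interest", with backward elimination at p < 0.1.

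Table 1 in section 1 includes a 2017 study of PCV13 alone, with groups "n=4 CLL + ibrutinib; n= 4 CLL - ibrutinib" and response rates "Ibrutinib 0%; No Ibrutinib 100" per cent. Apart from that row and the title of the matching reference, ibrutinib is not mentioned.

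**The concern.** The plan collects chemotherapy, which Table 1 links to poorer response, but does not collect ibrutinib, for which Table 1 shows the sharpest contrast of any row. Patients on ibrutinib or another unlisted therapy may enrol. With no item of its own, the therapy leaves a patient's treatment entries identical to those of an untreated patient. If a site enters it under chemotherapy, a term the protocol does not define, the patient is merged with that group.

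Two things are at stake, both in the secondary factor analysis:

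- **Description.** The study could not say how these patients respond to the sequential schedule, although section 1 says the schedule's efficacy in CLL is unknown.
- **Adjustment.** The odds ratios for chemotherapy and anti-CD20 could absorb part of the unrecorded therapy's effect, but only if its use differs between the groups compared.

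**Working it through.** **1. Reproduce the Table 1 figure.** The inputs are 4 patients per group and response rates of 0% and 100%. So 0% × 4 = 0 and 100% × 4 = 4, that is 0/4 against 4/4, and 4 + 4 = 8 matches the stated N.

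**2. Strength of that evidence.**

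- Two-sided Fisher exact test: 2 / C(8,4) = 2/70 = 0.029.
- Clopper-Pearson upper 95% limit for 0/4: 1 − 0.025^(1/4) = 0.602. The lower limit for 4/4 is 0.025^(1/4) = 0.398. The intervals are therefore 0–60% and 40–100%.
- That study gave PCV13 only and required a 2-fold rise in 3 of 13 serotypes. This protocol requires a 4-fold rise in at least 70% of serotypes. The row is a reason to record the variable and gives no usable effect size.

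**3. What the listed items yield for three patients.**

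| Patient | Chemotherapy | Steroids | Anti-CD20 |
|---|---|---|---|
| Untreated | no | no | no |
| Ibrutinib only | no (or yes, if a site enters it there) | no | no |
| Chemotherapy only | yes | no | no |

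The second row always coincides with the first or the third. No analysis of these items can separate it.

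**4. Illustration of possible confounding.** Let p be the response without ibrutinib, the same with and without chemotherapy, so the true chemotherapy odds ratio is 1.00. Let π be the response on ibrutinib, and f0 and f1 the ibrutinib shares without and with chemotherapy. With odds(x) = x/(1 − x), the apparent crude odds ratio is

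odds[p(1 − f1) + πf1] / odds[p(1 − f0) + πf0].

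For p, two Table 1 rates from conjugate-vaccine rows in treatment-naive patients are used, 32% and 58.3%. Both rest on other response definitions, and the row giving 32% is inconsistent about which conjugate vaccine was used. The shares f0 and f1 are assumptions, because the documents give no case mix.

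Worked case: p = 0.32, π = 0, f0 = 0.10, f1 = 0.30. With chemotherapy, 0.32 × 0.70 = 0.224, odds 0.224/0.776 = 0.289. Without, 0.32 × 0.90 = 0.288, odds 0.288/0.712 = 0.404. The ratio is 0.71.

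Each cell gives the result for p = 32% / p = 58.3%:

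| Assumed shares f0 / f1 | π = 0 | π = 0, shares reversed | π = p/2 |
|---|---|---|---|
| 2% / 6% | 0.94 / 0.91 | 1.06 / 1.10 | 0.97 / 0.95 |
| 5% / 15% | 0.86 / 0.79 | 1.17 / 1.26 | 0.93 / 0.89 |
| 10% / 30% | 0.71 / 0.62 | 1.40 / 1.60 | 0.86 / 0.79 |
| 20% / 20% | 1.00 / 1.00 | 1.00 / 1.00 | 1.00 / 1.00 |

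These crude two-group values do not estimate the bias in the planned multivariable model.

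**5. What a descriptive result could deliver.** By the same exact formula, 0/10 gives a 95% CI of 0–31% and 0/20 gives 0–17%.

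**The case against.** The strongest case against has five parts.

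- **The form itself is not in the documents.** The electronic form may hold a field that the protocol does not list. That is fair, and the point is confined to the protocol's list. If the field exists, the correction is one line of text.
- **Section 6 is ambiguous.** Its reference to variables already mentioned may mean the section 5 list or only the three example factors in the sentence before. This is true, and the count of candidates depends on the reading. The conclusion does not: on either reading, treatment status can be built only from what is collected.
- **The effect on this cohort is unknown.** No document says how many such patients will enrol. Section 1 says vaccination is recommended "preferably before initiation of treatment", so the share may be low. The range in the table includes 1.00 and runs in both directions. This stands: confounding is shown to be possible, with neither its size nor its direction established. The descriptive loss does not depend on those assumptions, because it occurs if even one such patient enrols.
- **The evidence is thin.** Eight patients, another schedule and a looser definition support only a request to record the therapy. The documents hold no response data for other targeted agents. Both points stand.
- **A single pooled candidate mixes agents, and past with current use.** This is a fair limit on the regression term. Recording agent and dates allows past and current use to be separated in the description.

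**Conclusion.** The concern holds, with high confidence as to the protocol's list. Followed as written, the plan cannot report the response of patients on ibrutinib or other unlisted CLL therapy, or adjust for that therapy, although treatment status is one of the three factors section 6 names and Table 1 gives a direct reason to look.

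The consequence is limited to the secondary factor analysis and the description of the cohort. The primary serologic response rate, the protection rates and the geometric mean concentrations use no treatment item and are computed as before. Distortion of the chemotherapy odds ratio ranges from none or negligible to moderate under the assumed shares. It arises only if use of such therapy differs between the compared groups. The plan should be corrected, but the point does not threaten the primary result.

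**What to change.** **Minimum.** Add to the section 5 list one item for previous or current targeted or other CLL therapy, with agent, start date and stop date, determined before vaccination like the other treatment items. Report responders/n with an exact 95% CI for these patients.

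**Where numbers allow.** State in advance the minimum number of such patients, and include the item as its own candidate in the section 6 regression. If that level has no responders or only responders, use penalised (Firth) or exact logistic regression and apply the same p < 0.1 rule to its p-values. This could well be needed: if true response were 10% (an assumption), the chance of no responders would be 0.9^10 = 35% with 10 patients and 0.9^20 = 12% with 20.

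**Optional.** Record the start date of any CLL therapy begun between PCV13 and the post-vaccination sample.

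**Cost.** A few extra form fields and chart abstraction per patient, with no new patients, samples or procedures. If the regression starts from the section 5 list, the item is a 13th candidate beside 12: sex, smoking, age, comorbidity index, Rai stage, chemotherapy, steroids, anti-CD20, total IgG, lymphocytes, haemoglobin and platelets (pneumococcal IgG levels not counted). No sample size is stated, so with few such patients the coefficient may be uninformative and only the descriptive result usable. Penalised or exact regression may need software other than SPSS.

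### If a treatment group has no responders, the planned logistic model gives no finite odds ratio, and Wald-based removal would discard that factor however strong it is

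*Combined protocol and SAP*

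**What the plan says.** Section 6 (Data Analysis) makes factors associated with response a secondary outcome and gives age, treatment status and disease stage as examples. For these, "we will perform a multivariable logistic regression analysis, starting with all previously mentioned clinical variables of interest", "using a stepwise backward selection method based on p-value <0.1". On software, "we will use IBM SPSS version 24.0 (Chicago, Illinois) software".

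No penalised or exact form of the regression is named, so ordinary maximum likelihood is the natural reading. The plan does not say whether the removal p-value comes from the Wald or the likelihood-ratio test. It has no rule for a factor level in which nobody, or everybody, responds.

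The treatment variables in section 5 (Data collection) are past or ongoing chemotherapy, ongoing steroids, and past or ongoing anti-CD20 therapy. The laboratory definitions require at least a "4-fold increase in serotype specific anti-pneumococcal IgG for" at least 70% of serotypes. With nine serotypes measured, 0.70 × 9 = 6.3, so a responder needs at least 7 of 9.

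Two rows of Table 1 bear on the point. In a cohort of 32 given PPSV23, "87% had previous chemotehrapy and 73% anti-CD20", and the overall response was 0%. In a study of eight patients given PCV13, the result was "Ibrutinib 0%; No Ibrutinib 100"%, with four patients in each group.

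**The concern.** When one level of a binary factor contains no responders, the data are separated on that factor. The likelihood keeps rising as the coefficient moves towards minus infinity. The standard error grows faster than the coefficient, so the Wald statistic tends to 0 and its p-value to 1. Removal on that p-value discards the factor even when the evidence for it is strong. Under likelihood-ratio removal the factor stays, but is reported with an odds ratio of effectively zero and an unbounded Wald interval.

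This is not the general objection to stepwise selection: the full model, with nothing removed, also fails to give an estimate. Treatment status is one of the three factors named in section 6, and the Introduction says guidelines prefer vaccination before treatment starts. An adjusted estimate for treatment is therefore among the results readers will look for, and a strong treatment effect makes an empty cell more likely.

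**Working it through.** The plan gives no sample size, number of responders or treated fraction, so there is no figure of its own to reproduce. All counts and rates below are assumptions.

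**1. One factor, 0/15 exposed versus 25/85 unexposed responders**

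- *Maximum likelihood.* The exposed group contributes (1−p)^15, which is largest at p = 0, so no finite coefficient exists. After 20 Newton steps b = −20.3 and SE = 10378, giving z = −0.002 and Wald p = 0.998.
- *Likelihood ratio.* Fitted log-likelihood: 25 ln(25/85) + 60 ln(60/85) = −51.49. Null: 25 ln 0.25 + 75 ln 0.75 = −56.23. Twice the difference is 9.48 on 1 df, p = 0.002.
- *Firth.* This maximises the log-likelihood plus ½ log|I(β)|, where I is the information matrix. For a single binary factor it amounts to adding 0.5 to each cell: OR = (0.5/15.5)/(25.5/60.5) = 0.077. Profile-likelihood 95% CI 0.0006 to 0.61, p = 0.009.
- *Fisher exact.* p = 0.019.
- *Pearson chi-square.* 100 × (15 × 25)² / (15 × 85 × 25 × 75) = 5.88, p = 0.015 (0.036 with continuity correction).

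**2. Other assumed counts**

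| Responders, exposed vs unexposed | Wald p (20 steps) | Likelihood-ratio p | Firth OR | Firth p | Fisher p |
|---|---|---|---|---|---|
| 0/10 vs 10/40 | 0.999 | 0.025 | 0.138 | 0.086 | 0.18 |
| 0/12 vs 12/36 | 0.999 | 0.004 | 0.078 | 0.017 | 0.023 |
| 0/20 vs 20/60 | 0.998 | 0.0002 | 0.048 | 0.001 | 0.002 |

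The Wald result does not hinge on when the software stops. For 0/20 versus 20/60, p is 0.43, 0.86 and 0.998 after 6, 10 and 20 steps, always above 0.1.

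**3. With other covariates in the model**

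In 1000 simulated data sets (N = 80, about 25% treated, no treated responders by construction, five covariates including treatment), the treatment factor had p ≥ 0.1 in 100% of full-model fits by the Wald test and in 0% by the likelihood-ratio test.

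**4. How likely an empty cell is**

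With 100 patients, each exposed with probability 0.15, and true response rate r among the exposed, P(no exposed responder) = (1 − 0.15r)^100:

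- r = 2%: 0.997^100 = 74%
- r = 5%: 0.9925^100 = 47%
- r = 10%: 0.985^100 = 22%
- r = 22%: 0.967^100 = 3%

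For a fixed exposed group of size n the chance is (1−r)^n. With n = 10, 20 and 30 this is 60%, 36% and 22% at r = 5%, and 35%, 12% and 4% at r = 10%.

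**5. What the Table 1 zeros can support**

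The one-sided 95% upper limit for 0/n is 1 − 0.05^(1/n): 53% for 0/4 and 9% for 0/32.

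**The case against.** A reader might infer from Table 1 that an empty treated cell is to be expected. The table does not go that far.

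- The 0% in the pretreated cohort is for the whole cohort. The 13% without prior chemotherapy and the 27% without anti-CD20 did not respond either, so the row gives no treated-versus-untreated contrast. It also concerns PPSV23, with or without injections of a growth factor, and required a response to all six measured serotypes.
- The ibrutinib result is 0 of 4, which is compatible with a true rate up to 53%. Ibrutinib is not on the case report form list, so as planned it cannot enter the model.
- The two rows that link chemotherapy to response report a lower response, not none.
- Those results come from single-vaccine studies. The Introduction says the efficacy of the sequential schedule in CLL is unknown.

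These points stand. On the other side, the study's definition (4-fold in at least 7 of 9) is stricter than the 2-fold rise in 3 of 13 serotypes of the ibrutinib study. An empty cell remains plausible if the treated group is small and responds poorly.

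A reader might also infer that the analysis would reverse the message about vaccinating before treatment. That does not follow. The removal test is not named, so loss of the factor is conditional on Wald removal. The planned chi-square test, if applied to response by treatment, would show the crude difference in the worked example (p = 0.015). A standard error of 10378 would also alert the analyst. What the chi-square test cannot give is the adjusted estimate.

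Finally, separation is not the only reason a factor would be lost. In 600 simulated runs per rate with five null covariates, Wald removal dropped the factor in 76% of runs at a 5% treated rate, of which 49 percentage points came from empty cells. At 10% it was 78%, with 21 points from empty cells, and likelihood-ratio removal dropped it in 43%. Much of the loss at the higher rate is low power and the conservatism of the Wald test in small groups. The change proposed here will not cure low power.

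A lighter remedy is arguable: name the removal test, tabulate by level, and state a fallback for empty cells. Firth for all fits is preferable because the method is then fixed before the data are seen, and its cost is small.

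**Conclusion.** The point holds in conditional form. Given an empty cell in a treatment factor, the planned model cannot report that factor's adjusted effect: Wald removal discards it, and likelihood-ratio removal retains it without a finite odds ratio or usable Wald interval. That much follows from the method and needs no assumption about the data beyond the empty cell.

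How often it will happen cannot be settled from the documents. Under the assumed 100 patients with 15% exposed, the chance runs from about 74% at a 2% treated response rate to about 3% at 22%. The assumed cohort size, exposed fraction and rates all drive that range.

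The consequence is confined to the adjusted factor analysis, a secondary outcome. The primary serologic response rate is untouched.

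**What to change.** In section 6:

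1. State that the factor model is fitted by Firth penalised likelihood, with profile-likelihood 95% confidence intervals and p-values.
2. If removal by p-value is kept, state that it uses the (penalised) likelihood-ratio test and not the Wald test.
3. Tabulate responders/total for every level of every factor, and add a Fisher exact p-value where a level has 0% or 100% responders.

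The cost is a few sentences of analysis text, one routine outside the built-in SPSS procedure, and mild shrinkage of the estimates towards the null. No change to data collection is needed.
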